## Measurement Selection Rationale

Study measures have all proven sensitive and specific in our research with HCT survivors, except Knowledge of Survivorship Needs which is in testing. Most are standardized measures with population norms. Measures were selected to target outcomes or as descriptive variables or mediators or moderators of outcomes as defined by the aims.

## Measurement Time Points

The measures and their administration time points for three of the four assessments are listed in Table 1: baseline, 3 and 12 months. For group 1 intervention participants only, there will also be a brief orientation call for the study at 2 weeks, and an assessment at 6 weeks, that determines distress and knowledge of survivor health risks. Distress is measured on a 0-10 distress thermometer rating scale (0=no distress, 10=extreme distress) is >5, along with the first 2 items on the PHQ scored <=2 indicating low distress and depression symptoms. The distress thermometer is a widely used, validated and reliable measure of distress in cancer survivors.[144-147] Knowledge of HCT Survivor Health Risks is an 11-item screening for cardiometabolic and subsequent malignancy risks. Items are scored 0 ('my risk is higher') or 1 ('my risk is not different' or 'not sure') with a score >2 indicating inadequate knowledge of risks and eligibility for telehealth stepped care. The third criterion is whether the participant has viewed at least 3 pages of the online INSPIRE site. If any one of these 3 progress criteria are not met, intervention participants are stepped into telehealth self-management contact as described in Treatment section 7.5.1.

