### Primary Aims

1. Determine whether 2-5 year HCT survivors with elevated cancer-related distress or poor health care adherence, adherence to cardiometabolic or subsequent malignancy surveillance who are randomized to receive the online, patient-centered, self-management stepped care program will report reduced distress, and improved health care adherence for cardiometabolic or subsequent malignancy surveillance at 12 months when compared with an active control group who receive access to HCT survivorship best practices.
2. Determine characteristics of intervention participants who require telehealth stepped care at 6-weeks because they 1) do not meet criteria for adequate knowledge of subsequent malignancy and cardiometabolic risks, or 2) do not report improved distress, or 3) have not logged in to the online program.
3. Determine resources that would be needed to sustain the intervention as a national HCT survivorship program if implemented through the CIBMTR//NMDP.

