*Stepped Care Self-Management Telehealth Contacts.* Group 1 intervention participants who at the T2 (6 weeks) indicate no use of the online program, or lack knowledge of their cardiometabolic or subsequent malignancy risks, or do not indicate improvement in distress, will receive telehealth contacts. These will be three to four calls via phone. Calls will last 20-30 minutes for the first call and 10-20 minutes for the 'booster' calls. They will be led by a 'coach' trained by the clinical investigators in HCT and self-management skills, using a manual to deliver call content focused on assisting survivors with using the self-management skills in the online program. This is a brief, manualized intervention is designed to be sustainable without extensive clinical training and has been tested. The first session will focus on impairments indicated by the T2 6-week screening PRO. The coach and participant will make shared decisions, led by the participant, on goals and an action plan for addressing deficits, and elicit potential barriers and their solutions based on chronic disease self-management models (Figure 1).[1, 84, 133, 140-143] The second and third 'booster' calls will review progress on the action plan, address barriers and agree on a revised plan if needed. Participants and coaches will decide whether a fourth call would be helpful based on the complexity and difficulty of the goals and action plans. The contacts will be audiotaped for process evaluation

of content and fidelity to the self-management script.

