### Secondary Hypotheses

**Aim 2:** Determine characteristics of intervention participants who require telehealth stepped care at 6-weeks.

**Hypothesis 2:** Characteristics of intervention arm participants at the 6-week interim assessment who require telehealth stepped care because they 1) do not meet criteria for adequate knowledge of cardiometabolic risks, or 2) do not report improved distress, or 3) have not logged in to the online program will include those with higher depression or distress scores at baseline, more health care barriers at baseline, age 70+ years, male sex, people of color, lower income and education.

**Aim 3:** Determine resources that would be needed to sustain the intervention as a national HCT survivorship program if implemented through the CIBMTR//NMDP.

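### The 6-week rule for stepping participants up to telehealth calls has a distress cut that does not parse, and other sections state different distress and website-use criteria

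*Combined protocol and SAP*

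**What the plan says.** The operational rule is in Measurement Time Points. Group 1 intervention participants are assessed at 6 weeks on three things.

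- **Distress.** A thermometer runs from 0 (none) to 10 (extreme). The sentence then continues that the score "is >5, along with the first 2 items on the PHQ scored <=2 indicating low distress and depression symptoms".
- **Knowledge.** Eleven risk items are scored, "with a score >2 indicating inadequate knowledge of risks and eligibility for telehealth stepped care".
- **Use.** The third criterion is "whether the participant has viewed at least 3 pages of the online INSPIRE site".

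The section concludes: "If any one of these 3 progress criteria are not met, intervention participants are stepped into telehealth self-management contact".

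Other sections describe the same decision differently. Under Treatment (Intervention: Full Internet Program Access), the 6-week assessment sends calls to those in the Group 1 intervention arm who "indicate no use of the online program, or lack knowledge of their cardiometabolic or subsequent malignancy risks, or do not indicate improvement in distress". In Primary Aims, Aim 2 concerns those who lack adequate knowledge, or "do not report improved distress, or 3) have not logged in to the online program". Hypothesis 2 repeats this in Secondary Hypotheses ("do not report improved distress, or 3) have not logged in to the online program will include those with higher depression") and again in the tests of the specific aims. The Introduction twice describes the calls as being for people who have not improved by 6 weeks.

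The Analysis Plan for Hypothesis 2 makes the need for stepped care at 6 weeks a binary endpoint, analysed over the intervention arms of both Group 0 and Group 1. The plan for Aim 3 costs the calls separately, for Group 1 only.

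**The concern.** A decision threshold should allow two people with the same data to reach the same decision. This one does not, for three reasons. The distress sentence has no clear direction and does not say how the thermometer and the PHQ items combine. The section with the cut-points uses a score at one time, while every other statement of the rule uses a change. The use criterion has two thresholds.

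The decision allocates the telehealth component of the intervention tested in Aim 1. It is also the dependent variable for Aim 2 and feeds the telehealth costs in Aim 3. If the endpoint is built from a different rule than the one Hypothesis 2 describes, the profile of people needing calls will not answer the question asked. A programme intended for national use also needs one rule that others can reproduce.

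**Working it through.** The plan states no figure to reproduce, so the check sets the statements side by side and works out what each reading does.

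**1. Statements of the rule**

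| Section | Distress criterion | Use criterion |
|---|---|---|
| Measurement Time Points | 6-week score | three or more pages |
| Treatment | lack of improvement | any use |
| Primary Aims; Hypothesis 2 (both places) | lack of improvement | login |
| Introduction | lack of improvement (general) | not given |

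**2. The distress cut.** Assume whole-number thermometer scores 0 to 10 and a sum of the two PHQ items from 0 to 6 (the documents do not give this range). That makes 11 × 7 = 77 score pairs.

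- Literal reading, criterion met if thermometer >5 and PHQ items ≤2: 5 × 3 = 15 pairs.
- Probable reading, met if thermometer ≤5 and PHQ items ≤2: 6 × 3 = 18 pairs.
- A third possible reading, step up only if both scores are high: met in 77 − 5 × 4 = 57 pairs.

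No pair meets both the literal and the probable criterion, so these two disagree on 15 + 18 = 33 pairs. They agree on the other 11 × 4 = 44, where the PHQ items exceed 2 and both step the person up. At the extremes with PHQ items 0, the literal reading gives calls at thermometer 0 and none at thermometer 10. These are counts of score pairs, not proportions of patients.

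**3. Level or change.** Table 1 lists the CTXD and PHQ-8 at baseline but not the thermometer. Measurement Time Points does not list the CTXD at 6 weeks. No section names an instrument measured at both times for this purpose, or defines improvement. The difference can matter for people who enter Group 1 through poor adherence. On the plan's projections, 305 − 197 = 108 of Group 1 do not have elevated CTXD, or 108/2 = 54 in the intervention arm if allocation is equal. An improvement rule could step such people up because they had little distress to lose; a level rule generally would not.

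**4. Use.** Someone who logged in and viewed one or two pages fails the criterion in Measurement Time Points and passes it under Treatment, Primary Aims and Hypothesis 2. Process Measures lists a single visit and a three-page view separately, so the protocol itself distinguishes the two.

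**5. Who is exposed.** The Design section expects about 305 in Group 1. With equal allocation (assumed; Table 3 shows equal arms, 71 and 86 each), 305/2 = 152.5, about 152, are subject to the rule. Distress alone decides only for those with a knowledge score ≤2 and at least three pages viewed. Among them, the literal and probable readings conflict only when the PHQ items are ≤2.

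**6. What each reclassification costs.** Treatment plans three to four calls: "Calls will last 20-30 minutes for the first call and 10-20 minutes for the 'booster' calls". Three calls take 20 + 2 × 10 = 40 to 30 + 2 × 20 = 70 minutes. Four take 20 + 3 × 10 = 50 to 30 + 3 × 20 = 90 minutes, with the fourth at booster length. Each person reclassified therefore gains or loses an offer of 40 to 90 minutes of coach time.

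**7. Group 0.** The 6-week assessment and the calls are for Group 1 intervention participants only. The Aim 2 analysis nevertheless includes the Group 0 intervention arm, for whom the rule yields no value.

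**The case against.** The best defence is that the intent is recoverable. The thermometer anchors stand in the same sentence, the neighbouring knowledge cut uses a greater-than sign as the step-up direction, and every other section sends calls to people who are not doing well. The label of low distress may attach only to the PHQ items. On this view the aims and treatment text are summaries, and Measurement Time Points governs because it alone has cut-points.

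Much of this stands. A reader might infer that calls went to people with low distress and were withheld from people with high distress. The documents do not support that: it is one parse of an ungrammatical sentence, and nothing shows that it was programmed. A reader might also infer that improvement could be computed only from the two PHQ items. That is too strong, since Table 1 may not be exhaustive (physical function is a secondary outcome in Secondary Aims but has no row), and a direct report of change is conceivable.

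The defence does not remove the defect. Even with >5 as the trigger, the sentence does not say how the two scores combine. No section says which statement governs, and a level and a change are different criteria.

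**Conclusion.** The point holds as an error in the wording and consistency of a decision rule, and the sponsor should correct it. The 6-week distress criterion cannot be applied as printed, the other sections use a different concept of distress, and the use threshold differs for people who viewed one or two pages.

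About 152 people are subject to the rule, on the plan's projection of 305 and assumed equal allocation. That is the number exposed, not the number misclassified. The latter cannot be computed, because the documents give no 6-week distribution of thermometer, PHQ, knowledge or page-view results. Taking ≤5 as the intended low-distress cut is also an assumption.

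The consequences fall on who is offered calls, on the Aim 2 endpoint and on telehealth costs. A reader might infer that the Aim 1 comparison is invalid. It is not: the 12-month endpoint definitions (CTXD below 0.9, HCA-cardio at least 80%), the alpha split, the sample size and the intent-to-treat comparison do not depend on this rule.

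**What to change.** - In Measurement Time Points, state that the distress criterion is met only if the thermometer is ≤5 and the first two PHQ items are ≤2, and that anyone else is stepped up. Say whether ≤2 refers to the sum of the two items.
- Have the sponsor confirm both the cut at 5 and that a 6-week level, not change from baseline, is intended. This is a substantive choice. If change is intended, the plan must name an instrument measured at both times and define improvement.
- Name Measurement Time Points as the governing rule, with its three-page threshold, which Process Measures and the Hypothesis 1 engagement analysis already use. The one-page example in Secondary Analyses defines a utilization subgroup and should be kept distinct.
- Align the Introduction (both statements), Primary Aims, Treatment, Secondary Hypotheses and the restated Hypothesis 2.
- In the Analysis Plan for Hypothesis 2, define the endpoint by this rule and restrict it to the Group 1 intervention arm.
- Check the programmed 6-week rule against the corrected text.

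The cost is a wording amendment and a programming check. No new data collection is needed if the level rule is confirmed.

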## Baseline and Outcome Assessments

After consent, survivors will be directed to the 30-40 minute online baseline assessment. Measures are listed in Table 1. They will have the option to return to the assessment, if it has not been completed. This process will be repeated at 3 and 12-month outcome assessments. If the assessment is not completed, the NMDP study coordinators will contact the participant by phone and determine whether the assessment can be completed on the internet, if not, whether the assessment can be completed by mail.

## Patient Reported Outcomes (PRO)

### Primary Outcomes

*Cancer and Treatment Distress (CTXD)*. The CTXD is a 22-item inventory of distress or worry related to stressful events for cancer survivors.[25] The measure was developed by the PI from structured interviews with HCT patients, nurses and physicians and has been tested with long-term survivors (N=1978). Testing supports its value as a predictor of health outcomes and it has been used in several RCTs.[6, 148-150] Internal reliability for HCT survivors is  $\alpha = .93$ . There are 6 reliable subscales: uncertainty, health burden, family strain, finances, medical demands, identity.[151]

*Health Care Adherence (HCA)*. The HCA is derived from the Cornell Service Index.[152] We have tested the format with several thousand HCT survivors.[153] Scores are transformed to proportion of HCA recommendations met. For a primary outcome, we use HCA items reflecting adherence to cardiometabolic surveillance (HCA-cardio; 5 items). Additional items measure adherence to subsequent malignancy surveillance (HCA-cancer; 7 items) and will be a secondary endpoint (see below). Items are adjusted for sex and age at which tests are recommended. An item is scored as 'adhered to' if the participant is under the age of recommended test onset. Cut point for determining adherence for each item is based on the frequency of testing recommended in guidelines (annual, every 3 or 5 years). Score is calculated as percentage of tests completed. Since adherence is important to reduce mortality risk, we set the cutoff for not meeting adherence criteria at <80%. In our previous 6-site INSPIRE study, we found 34% not adherent to HCA-cardio surveillance using the above criteria. Validity for HCA-cardio is supported by the following associations ( $p<.01$  for all):

HCA-cardio was higher in those with self-reported high blood pressure, diabetes, history of heart attack, and those told they had cardiomyopathy or atherosclerosis. Discriminant validity is supported by no significant association of HCA-cardio with report of a history of second cancers, osteoporosis, or thyroid problems. The 21 Barriers to HCA items were defined from qualitative patient reports of HCT survivors.[154] With 6 subscales, the overall and subscale reliabilities are all  $\alpha > 0.80$ . Mean score with cut point  $>0.45$  will be used as an Aim 2 predictor. with subscales: Cost, Avoidance, Time, Knowledge, Provider Access, .

## Secondary Outcomes

Patient Health Questionnaire (PHQ-8). The 8 item PHQ8 scale is highly reliable, valid and widely utilized in medical and psychiatric studies.[155-157] We have extensive data documenting reliability and utility in survivors.

Health Care Adherence for subsequent malignancies. As described above, our assessment of HCA includes 7 items measuring adherence to surveillance for subsequent malignancies. Scoring will be carried out as described for the primary HCA-cardio outcome and will use a cutoff for not meeting adherence criteria at  $<80\%$ . In our previous 6-site INSPIRE study, we found 45% not adherent to HCA-cancer surveillance using the above criteria. Validity for HCA-cancer is supported by a marginal association with history of second cancer, with a 17% cumulative incidence rate in study participants (62% adherent vs. 54% occurrence rate for second cancers in the early post-HCT period;  $p = .074$ ).

## Moderators for Primary Outcomes and Risk Factors for Secondary Analyses

Background. Standard questions will define demographic characteristics including age, income, rural/urban by zip code, gender, ethnicity, education, work status, current medications, and cancer history.

Comorbidity Index and General Health. The self-report comorbidity index has strong kappa agreement with the Charlson comorbidity index, which is scored from medical records. Studies document the accuracy of HCT survivor self-report of medical diseases and problems when compared with medical records.[165][166] Medications will also be reported. It has documented validity and test-retest reliability, and used in our previous studies.[165-167]

GVHD Symptom Scale. For allogeneic HCT recipients, a reliable, validated measure based on cGVHD severity; type and duration of medications for cGVHD.[168]

## Mediators for Primary Outcomes

Knowledge of Health Care Needs. This 15-item measure addresses 2 factors: 1) knowledge of treatment and related risks, including cardiometabolic and second cancer risks, and 2) understanding of health care recommendations and emotional health resources after HCT as included in our intervention. With N=936 participants in our previous INSPIRE study, alpha is strong for the overall score ( $\alpha = .92$ ) and factors ( $\alpha = .82$ ,  $\alpha = .93$ ). The measure is derived from a similar measure developed in our SCOEN collaborations.[82]

Health Related Self-Efficacy. This measure reflects beliefs about health-related self-efficacy.[169, 170] In testing with N=860 HCT survivors, the measure has reliability of  $\alpha = 0.86$ .

### Cost and Resource Tracking

We will track the costs of maintaining the program if disseminated (not including elements required for research implementation) as indicated by 1) materials, 2) programming for site maintenance, technical problem solving, and updating content and maintaining social networking, 3) multi-center staff time for identifying, approaching and tracking participants, and responding to participant comments 4) coordinating center and CIBMTR/NMDP staff time for tracking participants, responding to participant comments and requests, and responding to technical problems. We will track costs separately for the self-management call component. Site staff will report cost summaries quarterly. These will be standardized to report the cost per participant who reaches at least one of the primary endpoints for the study, specified for each type of cost (materials, staff time) as well as total costs. Because we will track the costs of preparing SCPs and internet links provided to the control group and will know their outcomes, we will also be able to calculate an incremental cost-effectiveness ratio for the internet intervention program compared to the control cost-effectiveness, similar to the method described by Mandelblatt and colleagues.[171, 172]

### Medical Records

For cohort description and covariates, diagnoses and treatment-related variables will be downloaded or abstracted from the participating transplant center medical records.

### Internet data security

The study internet site from the previous INSPIRE research project underwent review with and met specifications from the Information Security Office at Fred Hutch in July 2019. Fred Hutch developed a secured patient portal, to secure the identities of participants and their data. To protect the privacy of patient data, once participants 'submit' their assessment responses or two weeks go by without activity, assessments completed are permanently secured behind a firewall and cannot be accessed again. The same site and portal will be used in the current project, with updated content.

## **9.0 DRUGS, IRRADIATION AND MARROW/STEM CELL ADMINISTRATION TOXICITIES AND COMPLICATIONS**

Not applicable.

## **10.0 GUIDELINES FOR ADVERSE EVENT REPORTING**

### Adverse Event Reporting/Institutional Policy

The following guidelines are the minimum Cancer Consortium IRB adverse event (AE) reporting guidelines. Protocol-specific additional reporting requirements for adverse events are addressed in Section 10.2. In

accordance with institutional policy, all adverse events which in the opinion of the principal investigator are unexpected and related or possibly related to the research and serious or suggest that the research places research participants or others at greater risk of physical or psychological harm than was previously known or recognized be reported to the IRB within 10 calendar days of learning of the problem.

Institutional support of trial monitoring will be in accordance with the Fred Hutch/University of Washington Cancer Consortium Institutional Data and Safety Monitoring Plan. Under the provisions of this plan, Fred Hutch Clinical Research Support coordinates data and compliance monitoring conducted by consultants, contract research organizations, or Fred Hutch employees unaffiliated with the conduct of the study. Independent monitoring visits occur at specified intervals determined by the assessed risk level of the study and the findings of previous visits per the institutional DSMP. Independent monitoring meetings occur annually or more often as determined by the findings of the previous meetings (see DSMB charter.)

Definitions:

**Adverse Event** - Any untoward medical occurrence in a patient or clinical investigation subject administered a pharmaceutical product, medical treatment or procedure and which does not necessarily have to have a causal relationship with this treatment. An adverse event can therefore be any unfavorable and unintended sign (including an abnormal laboratory finding, for example), symptom, or disease temporally associated with the use of a medicinal product, medical treatment or procedure whether or not considered related to the medicinal product.

**Life-threatening Adverse Event** – Any adverse event that places the patient or subject, in view of the investigator, at immediate risk of death from the reaction.

**Unexpected Adverse Event** – An adverse event is “unexpected” when its nature (specificity), severity, or frequency are not consistent with (a) the known or foreseeable risk of adverse events associated with the research procedures described in the Protocol-related documents, such as the IRB-approved research protocol, informed consent document and other relevant sources of information such as product labeling and package inserts; and are also not consistent with (b) the characteristics of the subject population being studied including the expected natural progression of any underlying disease, disorder or condition any predisposing risk factor profile for the adverse event.

**Serious Adverse Event (SAE)** – Any adverse event occurring that results in any of the following outcomes:

- death
- a life-threatening adverse event (real risk of dying)
- inpatient hospitalization or prolongation of existing hospitalization
- a persistent or significant disability/incapacity
- a congenital anomaly
- requires intervention to prevent permanent impairment of damage

**Attribution** - The following are definitions for determining whether an adverse event is related to a medical product, treatment or procedure:

- An adverse event is “**related or possibly related to the research procedures**” if in the opinion of the principal investigator, it was more likely than not caused by the research procedures.
- Adverse events that are solely caused by an underlying disease, disorder or condition of the subject or by other circumstances unrelated to either the research or any underlying disease, disorder or condition of the subject are not “related or possibly related.”
- If there is any question whether or not an adverse event is related or possibly related, the adverse event should be reported.

The Cancer Consortium Expedited Reporting Form should be completed for all adverse events that meet the expedited reporting requirements. The AE form should be faxed to the IRO at [contact]. All available information should be submitted.

